2.4.6.2 Analyses of pharmacokinetic variables

Non-compartmental analysis for PK parameter estimation in East Asian patients from East Asian sites is described in this analysis plan. Population PK analysis is planned for all patients in the study and will be described in a separate population PK analysis plan.

Pharmacokinetic parameters to be estimated using noncompartmental analysis include, but will not be limited to: maximum plasma concentration (C_{max}), time to maximum plasma concentration (t_{max}), elimination half-life ($t_{1/2\beta}$), area under the concentration-time curve (AUC), apparent clearance (CL/F), and apparent volume of distribution (V/F). Other parameters may be calculated, if deemed necessary. PK analysis is not in the scope of this SAP and would be reported separately.

2.4.7 Analyses of exploratory endpoints

2.4.7.1 TSQM-9

The Treatment Satisfaction Questionnaire for Medication (TSQM) version 9 assesses patient satisfaction with treatment. The TSQM Scale scores, and their changes from baseline in the factor or BPA prophylaxis period and fitusiran treatment period are summarized descriptively.

2.4.7.2 HAL and pedHAL

The Haemophilia Activities List (HAL, in patients ≥ 18 years of age) and pediatric HAL (pedHAL, in patients < 18 years of age) questionnaires assess subjective functional ability to perform activities of daily living. Overall score, component scores, domain scores, and their changes from baseline in the factor or BPA prophylaxis period and fitusiran treatment period are summarized descriptively.

2.4.7.3 EQ-5D-5L

The EQ-5D-5L is a standardized instrument for use as a measure of QOL outcome. Index value and visual analogue scale (VAS) score and their changes from baseline in the factor or BPA prophylaxis period and fitusiran treatment period are summarized descriptively. Numbers and percentages of patient by level and dichotomized level (1 = no problems, 2 to 5 = “problems”) of each dimension are reported.

2.4.7.4 Haemo-QOL

The Haemo-QOL will be provided to patients <17 years of age. The change from baseline in total score of Haemo-QOL in the factor or BPA prophylaxis period and fitusiran treatment period are analyzed using a mixed model for repeated measure analysis (MMRM) with a robust sandwich covariance matrix, with fixed effects of study period (factor or BPA prophylaxis period and fitusiran treatment period), baseline Haemo-QOL total score for each treatment period as covariates. Domain scores for Haemo-QOL and their changes from baseline are summarized descriptively. Only the descriptive statistics are provided if MMRM model does not converge due to the small sample size.

2.4.7.5 HJHS

Joint health status is assessed via the HJHS, as administered by a healthcare professional trained in the use of anthropometric measures. Response is summarized. If the joint score is evaluated within 2 weeks after a joint or adjacent muscle bleeding episode or a surgery is performed on a joint and the joint score is evaluated from start date of surgery to the end of perioperative procedure period + 7 days, then the data for that joint will be excluded. A sensitivity analysis excluding the non-evaluable results will be performed.

2.4.7.6 Number of target joint bleeding episodes

An exploratory analysis of the number of target joint bleeding episodes may be performed using the same negative binominal model as the primary analysis.

2.4.7.7 Incidence and titer of antidrug antibodies to fitusiran in the fitusiran treatment period

The ADA analysis will be based on all patients in the safety analysis set with at least one post baseline ADA result in fitusiran prophylaxis period. Number of patients testing positive for ADA pre-study-drug (baseline positive) and post-study-drug administration are summarized by Hemophilia type (A/B) and incidence of ADA positivity is presented by frequency and as a percent by Hemophilia type and across all patients. In addition, maximum ADA titer and range of titer values are presented by Hemophilia type and across all patients.

2.4.7.8 AT activity level over time

Please refer to [Section 2.4.6.1.1](#).

2.4.7.9 Thrombin generation over time

Please refer to [Section 2.4.6.1.2](#).

2.4.7.10 Fitusiran plasma levels

Fitusiran plasma concentrations and PK parameters including but not limited to C_{max} , t_{max} , $t_{1/2\beta}$, AUC, CL/F, and V/F will be summarized descriptively.

2.4.7.11 Change in patient resource use (eg, work/school attendance, visits to doctor/hospital)

Change in patient resource use (eg, work/school attendance, visits to doctor/hospital) from baseline in the factor or BPA prophylaxis period and fitusiran treatment period are summarized descriptively.

2.5 DATA HANDLING CONVENTIONS

2.5.1 General conventions

All data listings that contain an evaluation date will contain a study day relative to the first dose date of fitusiran, which is designated as Day 1. Study days after first dose date of fitusiran will be calculated as evaluation date - first dose date +1 and study days before first dose date of fitusiran will be calculated as evaluation date -first dose date. For example, the day prior to first dose date of fitusiran will be Day -1 and the day after first dose date of fitusiran will be Day 2, etc. There will be no Study Day 0.

Categorical variables will be summarized using counts and percentages. Continuous variables will be summarized using the number of patients (n), mean, SD, median, interquartile range (Q1, Q3), minimum value (min), and maximum value (max). The precision of the measurement for each continuous variable will be used to determine the number of decimal places to present in tables, figures and derived listings. Minimum and maximum values will be reported with the same precision as the units of measure. The other statistics mean, median and SD will be reported to 1 greater decimal place. Any values that require transformation to standard units (metric or SI) will be converted with the appropriate corresponding precision.

2.5.2 Data handling conventions for secondary efficacy variables

Not Applicable.

2.5.3 Missing data

For categorical variables, patients with missing data are not included in calculations of percentages unless otherwise specified. When relevant, the number of patients with missing data is presented.

Handling of medication missing/partial dates

No imputation of medication start/end dates or times will be performed. If a medication date or time is missing or partially missing and it cannot be determined whether it was taken prior or concomitantly, it will be considered as a concomitant medication.

Handling of adverse events with missing or partial date/time of onset

Missing or partial adverse event onset dates and times will be imputed so that if the partial adverse event onset date/time information does not indicate that the adverse event started prior to treatment or after the treatment-emergent adverse event period, the adverse event will be classified as treatment-emergent. No imputation of adverse event end dates/times will be performed. These data imputations are for categorization purpose only and will not be used in listings. No imputation is planned for date/time of adverse event resolution.

Handling of adverse events when date and time of first investigational medicinal product administration is missing

When the date and time of the first dose of fitusiran is missing, all adverse events that occurred on or after the first day of fitusiran treatment period (M0/D1) should be considered as treatment-emergent adverse events. The exposure duration should be kept as missing.

Handling of missing assessment of relationship of adverse events to investigational medicinal product

If the assessment of the relationship to fitusiran is missing, then the relationship to fitusiran has to be assumed and the adverse event considered as such in the frequency tables of possibly related adverse events, but no imputation should be done at the data level.

Handling of missing severity of adverse events

If the severity is missing for 1 of the treatment-emergent occurrences of an adverse event, the maximal severity on the remaining occurrences will be considered. If the severity is missing for all the occurrences, a “missing” category will be added in the summary table.

Handling of potentially clinically significant abnormalities

If a patient has a missing baseline he will be grouped in the category “normal/missing at baseline.”

For PCSAs with 2 conditions, one based on a change from baseline value or a normal range and the other on a threshold value, with the first condition being missing, the PCSA will be based only on the second condition.

For a PCSA defined on a threshold and/or a normal range, this PCSA will be derived using this threshold if the normal range is missing; eg, for eosinophils the PCSA is >0.5 GIGA/L or $>$ upper limit of normal (ULN) if $ULN \geq 0.5$ GIGA/L. When ULN is missing, the value 0.5 should be used.

Measurements flagged as invalid by the laboratory will not be summarized or taken into account in the computation of PCSA values.

Handling of bleeding events with missing bleed/treatment time

On the eDiary device, it is not possible to leave questions unanswered or to enter partial date for bleeds or bleeding treatments.

In the bleeding diary pages of the CRF, it is possible to have missing time of a treatment or a bleed. In that case, it is assumed that the bleeds and treatments with missing time occurred at 12:00 am.

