2.1.3 Efficacy endpoints

2.1.3.1 Primary efficacy endpoint

Global protocol: The primary efficacy endpoint of the study is annualized bleeding rate (ABR) in the fitusiran efficacy period and the factor/BPA prophylaxis period.

US protocol: The primary efficacy endpoint of the study is annualized bleeding rate (ABR) in the fitusiran treatment period and the BPA prophylaxis period.

Bleeding Episode Definitions

The primary source of bleeding data is the eDiary. Additional bleeding data may be captured from the bleeding diary pages of the CRF, if not reported in the eDiary. Any other sources of bleeding data will be discussed in the CSR.

A bleeding episode is defined as any occurrence of hemorrhage that may require administration of factor or BPA infusion, eg, hemarthrosis, muscle, or mucosal bleeding episodes.

The start time of a bleeding episode will be considered the time at which symptoms of bleeding episode first develop. Bleeding or any symptoms of bleeding at the same location that occurs within 72 hours of the last injection used to treat a bleed or 72 hours after the start of an untreated bleed at that location will be considered a part of the original bleeding event, and will count as one bleeding episode towards the ABR. Any bleeding symptoms that begin more than 72 hours from the last injection used to treat a bleed or 72 hours after the start of an untreated bleed at that location will constitute a new bleeding event.

A spontaneous bleeding episode is a bleeding event that occurs for no apparent or known reason, particularly into the joints, muscles, and soft tissues.

Bleeding episodes sustained during sports and recreation will be counted as traumatic bleeding episodes.

Traumatic bleeds that occur in different locations simultaneously (same date/time) in the same patient will be considered as one bleeding episode. Spontaneous bleeds that occur simultaneously (same date/time) in different locations in the same patient will be considered as separate bleeds.

A joint bleeding episode is characterized by an unusual sensation in the joint (“aura”) in combination with 1) increasing swelling or warmth over the skin over the joint, 2) increasing pain or 3) progressive loss of range of motion or difficulty in using the limb as compared with baseline.

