A target joint is defined as a joint where 3 or more spontaneous bleeding episodes in a single joint within a consecutive 6-month period has occurred; where there has been ≤ 2 bleeding episodes in the joint within a consecutive 12-month period the joint is no longer considered a target joint.

Efficacy analysis will focus on observed data as collected, unless otherwise specified. Patients who discontinue study drug during the study will be strongly encouraged to continue study participation including the recording of bleeding episode data. Only bleeding episodes that are treated with BPA/factor will be included in the primary analysis of endpoints evaluating bleeding.

Annualized bleeding rate will be calculated as described in [Section 2.4.4.1.1](#).

Efficacy Period and factor/BPA prophylaxis Period

In the protocol, for the purpose of ABR calculation, the factor/BPA prophylaxis period and fitusiran “Onset Period”, “Efficacy Period” and “Treatment Period” are defined. The factor/BPA prophylaxis period is defined as the 6 months period before the first dose of fitusiran, during which patients continue their pre-study, regularly scheduled prophylaxis regimen with factor concentrates or BPAs. The Onset Period is defined as the first 28 days after the first dose of fitusiran, during which the AT lowering capacity of fitusiran is increasing but has not yet reached therapeutic levels. The Efficacy Period is defined as starting on Day 29 when the AT lowering capacity of fitusiran has achieved therapeutic target range. The Treatment Period is defined as the onset period plus the efficacy period. The window for each period is summarized in the table below.

Period	Definition
Factor/BPA prophylaxis period	Day -168 to the earlier of Day -1 or the last day of bleeding follow up
Fitusiran onset period	Day 1 to the earlier of Day 28 or the last day of bleeding follow up
Fitusiran efficacy period	Day 29 to the earlier of Day 190 or the last day of bleeding follow up
Fitusiran treatment period	Onset period plus the efficacy period

The last day of bleeding follow up is defined as the deactivation date captured in eDiary.

If a patient does not have bleeding episode data collected after Day 28 due to early study discontinuation in the fitusiran treatment period, the efficacy period will be from Day 1 to the earlier of date of study discontinuation and the last day of bleeding follow up.

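### Setting a missing CRF treatment time to 12:00 am can place a treatment before its own bleed and close the 72-hour episode window early

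*SAP*

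**What the plan says.** The eDiary is the primary source of bleeding data, and the CRF is a back-up (SAP 2.1.3.1): "Additional bleeding data may be captured from the bleeding diary pages of the CRF, if not reported in the eDiary". SAP 2.5.3 separates the two sources on missing times. For the eDiary: "On the eDiary device, it is not possible to leave questions unanswered or to enter partial date for bleeds or bleeding treatments". CRF entries, by contrast, can lack a clock time for the bleed or for its treatment, and for those the SAP's rule is: "it is assumed that the bleeds and treatments with missing time occurred at 12:00 am". The one value serves both fields. The SAP does not require a treatment to fall at or after the bleed it treats, and it plans no sensitivity analysis for the rule.

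The clock times then feed the episode count in SAP 2.1.3.1. At one location, the rule for a new event begins "Any bleeding symptoms that begin more than 72 hours from the last injection used to treat a bleed or 72 hours after the start", where the second limb refers to bleeds that received no treatment. The primary analysis is limited to treated bleeds: "Only bleeding episodes that are treated with BPA/factor will be included in the primary analysis of endpoints evaluating bleeding".

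**The concern.** Midnight is the earliest moment of the recorded date. If a bleed has a recorded time and its same-day treatment does not, the rule produces an order that cannot have happened: treatment first, bleed afterwards. The 72-hour window is measured from that treatment when it is the last one given, so the window starts before the bleed did. Symptoms that continue the same bleed can then fall outside it. If those symptoms are also treated, one episode enters the primary count as two.

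The stake is the accuracy of the numerator of the annualized bleeding rate for the few patients with such records. The text is a stated rule, so a programmer following it would produce this result.

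**Working it through.** **Inputs.** Missing times become 00:00 of the recorded date (SAP 2.5.3). The same-location window is 72 hours (SAP 2.1.3.1). The fitusiran efficacy period is Day 29 to Day 190, so 190 − 29 + 1 = 162 days, and the prophylaxis period is Day −168 to Day −1, or 168 days (SAP 2.1.3.1). Planned numbers are about 30 in Cohort A and 50 in Cohort B (SAP 1.1). Planning rates are those of SAP 1.3. The plan states no figure for this rule, so there is none to reproduce.

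**1. Order.** A bleed is recorded at 15:00 and its treatment that day has no time. The treatment is set to 00:00, and 0 − 15 = −15, so it sits 15 hours before its bleed. The inversion arises for any same-date bleed recorded after 00:00.

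**2. Window.** Let the true injection time be *u* hours after midnight. Measured from the true injection, the window is 72 − *u* hours. Since *u* is below 24, it can shrink to just over 72 − 24 = 48 hours. Example: injection at 20:00 on day 0, symptoms at the same location at 10:00 on day 3.
- True gap: 72 + 10 − 20 = 62 hours, same episode.
- Computed gap: 72 + 10 − 0 = 82 hours, new episode.

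**3. When it matters.** Let the later symptoms start *t* hours after midnight.
- Dates 2 days apart: the computed gap is 48 + *t*, at most 72, and the true gap is smaller. No error.
- Dates 4 days apart: the true gap is 96 + *t* − *u*, above 72, and so is the computed gap. No error.
- Dates 3 days apart: the computed gap is 72 + *t*, so the pair is split, yet the truth is one episode whenever *t* ≤ *u*. If both times are assumed independent and uniform over the day, 50% of such pairs are wrongly split. A simulation of 1,000,000 draws gave the same 50%, and 0 for the other two spacings.

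**4. The other direction.** If the later bleed has no time, the gap is understated. With an injection recorded at 08:00 on day 0 and a bleed truly at 20:00 on day 3, the true gap is 72 + 20 − 8 = 84 hours (new), but the computed gap is 72 − 8 = 64 hours (same). If both times are missing, the gap is exactly 72 hours, which is not more than 72, and the pair is merged. Under the same uniform assumption, 50% of pairs dated 3 days apart are wrongly merged in each case.

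**5. Using the bleed start instead.** Let the bleed start at *b* on the injection date, with *b* ≤ *u*. For dates 3 days apart, midnight wrongly splits when 0 < *t* ≤ *u*. The bleed start wrongly splits only when *b* < *t* ≤ *u*, which is part of that range. It adds no wrong merges, because the imputed time is never later than the true one. With the bleed of step 1 at 15:00, the example of step 2 gives 82 − 15 = 67 hours, correctly the same episode.

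**6. Scale of one episode.** For one patient over the full efficacy period: 365.25/162 = 2.25 on the annualized rate. For a cohort, expected bleeds are N × rate × days/365.25.

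| Period | Expected bleeds | One episode |
|---|---|---|
| Cohort A, fitusiran, rate 4 | 30 × 4 × 162/365.25 = 53.2 | 1.9% |
| Cohort B, fitusiran, rate 4 | 50 × 4 × 162/365.25 = 88.7 | 1.1% |
| Cohort A, prophylaxis, rate 12 to 16 | 165.6 to 220.8 | 0.6% to 0.5% |
| Cohort B, prophylaxis, rate 4 to 6 | 92.0 to 138.0 | 1.1% to 0.7% |

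These are the weights of a single episode at planning assumptions. They do not estimate how many episodes are affected.

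**The case against.** The best defence is that this is a simple, prespecified convention for a back-up source. The eDiary cannot leave a time blank, and sites review entries with patients at least every two weeks (Protocol 7.2.1), so the affected records may be few or none. The rule is the same in both within-patient periods, and dates are kept, so no bleed moves between study periods. Errors run both ways. All of this stands, and it keeps the point small. It does not explain why a treatment should be allowed to precede its own bleed when the bleed time is known.

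Three stronger readings are tempting and the documents do not support them.
- A reader might infer that every CRF-entered bleed is affected. The rule reaches only entries with a missing time.
- A reader might infer that a bleed whose treatment is placed before it becomes untreated and leaves the primary analysis. That needs linkage by clock time, and the SAP does not say how treatments are linked. Its summaries of injections and dose per bleed (SAP 2.4.4.2.7) sit more naturally with linkage by record. A bleed misclassed in this way would also still appear in the planned analysis of treated and untreated bleeds (SAP 2.4.4.1.3).
- A reader might infer that two untimed traumatic bleeds on one date are wrongly merged, under "Traumatic bleeds that occur in different locations simultaneously (same date/time) in the same patient will be considered as one bleeding episode". This requires different locations and both times missing, and counting such a pair once is arguable. Spontaneous bleeds are not merged: "Spontaneous bleeds that occur simultaneously (same date/time) in different locations in the same patient will be considered as separate bleeds".

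**Conclusion.** The point holds as a minor one. When a bleed has a recorded time and its same-date treatment does not, SAP 2.5.3 produces an impossible order. The 72-hour window closes up to 24 hours early, and a continuing bleed dated 3 days later can be counted as new. The number of such records is not given, so the total effect on the annualized bleeding rate cannot be computed; it is probably small. No direction of bias in the rate ratio is shown, because a missing time on the later bleed works the opposite way.

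The conclusion assumes that 12:00 am means the start of the recorded date, that the treatment truly followed the onset of its bleed, and that the imputed time is the one used in the 72-hour rule. The 50% figures also rest on uniform clock times and apply only to same-location pairs dated 3 days apart.

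**What to change.** Amend the paragraph on missing bleed and treatment times in SAP 2.5.3:
- Keep each treatment attached to its bleed by the CRF record.
- When a treatment time is missing and its bleed has a recorded time on the same date, impute the bleed start time instead of 12:00 am, so that no treatment precedes the bleed it treats.
- Report the number of records imputed.

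This does not remove every error. Symptoms on day 3 at a clock time between the bleed start and the true injection would still be split, and other missing-time cases stay as they are. Moving missing injection times to the end of the day is not a remedy: it exchanges wrong splits for wrong merges at about the same 50% rate. The traumatic-bleed rule needs no change on this account.

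The cost is one paragraph of derivation text and a count in the report. No new data are needed.

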2.5.4 Windows for time points

A scheduled measurement will be used if it is available. Otherwise, derived analysis visit window will apply to data collected on unscheduled visits and early withdrawal visits (such as PD, clinical laboratory parameter, vital signs, etc.) to re-allocate a post-baseline unscheduled measurement to a scheduled measurement, except for PK and ECG, using Study Day (defined in [Section 2.5.1](#)), according to the following allocation table:

Analysis visit label	Target study day	Derived Window in study days	
		Lower bound	Upper bound
Baseline for factor/BPA prophylaxis period	The last non-missing assessment before enrollment date	-INF	Enrollment date
Day -168	-168	1 day after enrollment date	-155
Day -140	-140	-154	-127
Day -112	-112	-126	-99
Day -84	-84	-98	-71
Day -56	-56	-70	-43
Day -28	-28	-42	-1
Baseline for fitusiran prophylaxis period	1	1	1
Day 15	15	2	21
Day 29	29	22	35
Day 43	43	36	49
Day 57	57	50	70
Day 85	85	71	98
Day 113	113	99	126
Day 141	141	127	154
Day 169	169	155	182

Analysis visit label	Target study day	Derived Window in study days	
		Lower bound	Upper bound
Day 197	197	≥183	EOS/ET visit date if EOS/ET visit is ≥183
Day 225	28 days after EOS/ET for patients who complete the AT F/U visits	1 day after EOS/ET visit	999
Endpoint	Last non-missing post-baseline assessment on or before EOS/ET visit		

If more than one data point is within a window the visit closest to the target study day will be selected. If there are multiple visits with the same distance from the scheduled visit day, the last value will be selected.

